## List of abbreviations

ADE	Adverse device effect
AE	Adverse event
AESI	Adverse event of special interest
AOI	Anatomical Areas of Interest
ATC	Anatomical Therapeutical Chemical
BDDE	1,4-butanediol diglycidyl ether
CDMS	Clinical Data Management System
CE	Conformité Européene (European conformity)
CI	Coordinating Investigator
CIP	Clinical Investigation Plan
CIR	Clinical Investigation Report
COVID-19	Corona Virus Disease of 2019
CRO	Contract Research Organization
CTR	Common treatment site responses
DCP	Data Cleaning Plan
DMP	Data Management Plan
DRM	Data Review Meeting
EC	Ethics Committee
eCRF	electronic Case Report Form
EU	European Union
ExC	Exclusion criterion
FAS	Full Analysis Set
FST	Fitzpatrick skin type
G	Gauge
GAIS	Global Aesthetic Improvement Scale
GCP	Good Clinical Practice
GDPR	General Data Protection Directive
HA	Hyaluronic acid
HIPAA	Health Insurance Portability and Accountability Act
IA	Interim analysis
IB	Investigator's brochure
ICF	Informed Consent Form
IDE	Investigational device exemption
IFU	Instructions for Use
IMD	Investigational medical device
IMDRF	International Medical Device Regulators Forum

# Croma

IRB	Institutional Review Board
ISO	International Organization for Standardization
IUD	Intrauterine device
IUS	Intrauterine hormone-releasing system
MDD	Medical Device Directive
MDR	Medical Device Regulation
MedDRA	Medical dictionary for regulatory activities
MNAR	Missing not at random
MVDSS	Midface Volume Deficit Severity Scale
NLF-SRS	Nasolabial Folds Severity Rating Scale
NPRS	Numerical Pain Rating Scale
PPS	Per-Protocol Set
PT	Preferred term
RT	Repeat Treatment
SADE	Serious adverse device effect
SAE	Serious adverse event
SAF	Safety Analysis Set
SAP	Statistical Analysis Plan
SARS-CoV-2	Severe acute respiratory syndrome coronavirus 2
SDV	Source data verification
SOC	System organ class
SOI	Symptoms of interest
SV	Screening Visit
TMF	Trial master file
TUP	Touch-Up Treatment
US(A)	United States (of America)
U(S)ADE	Unanticipated (serious) adverse device effect
WHO	World Health Organization
WOCBP	Women of childbearing potential
US(A)	United States (of America)
3D	Three-dimensional

## Glossary

Definitions of terms used in this Clinical Investigation Plan are in accordance with ISO 14155:2020 if not indicated otherwise (e.g., study-specific definitions). Some of the definitions may be defined under national regulations. Therefore, there may be the need to check for definitions written down in regional / national guidance documents or regulations can:

Adverse Device Effect (ADE)	Adverse event related to the use of an investigational medical device. This definition includes				
	
 
adverse events resulting from insufficient or inadequate instructions for use, deployment, implantation, installation, or operation, or any malfunction of the investigational medical device.
 
any event resulting from use error or from intentional misuse of the investigational medical device.
 
the 'comparator' if the comparator is a medical device.
 
				
Adverse Event (AE)	An adverse event (AE) is defined as any untoward medical occurrence, unintended disease or injury, or untoward clinical signs (including abnormal laboratory findings) in subjects, users or other persons, whether or not related to the test device (IMD) or comparator device and whether anticipated or unanticipated.				
	This definition includes events related to the test device or the comparator and events related to the procedures involved.				
	For users or other persons, this definition is restricted to events related to the use of test device or comparator device.				
	Study-specific addition: AEs initially observed beyond baseline treatment or worsening of pre-existing AEs are defined as treatment-emergent AEs (TEAEs).				
(serious or non-serious) - Adverse Events of Special Interest (AESI) (study-specific definition)	AESIs are defined as scientific and medical concern specific to the sponsor's product or program, for which ongoing monitoring and rapid communication by the investigator to the sponsor could be appropriate. Such events may require further investigation in order to characterize and understand them. Depending on the nature of the event, rapid communication by the sponsor to other parties may also be needed. AEs of special interest are defined in section 14.1.				
Blinded evaluator at the site (study-specific	Only responsible for live MVDSS, NLF-SRS and modified GAIS evaluations at the site.				
definition)	Note: The blinded evaluator at the site is not blinded for treatment allocation during the repeat-treatment phase. However, he/she will be still blinded for the treatment a subject received during the initial treatment phase until final database lock.				
Blinding	Blinding is a procedure in which one or more parties to the clinical investigation are kept unaware of the treatment assignment(s). This clinical investigation is termed 'evaluator blind', i.e., at least the primary endpoint is assessed without knowledge of whether an IMD or comparator has been used to treat a subject.				
Case Report Form (CRF)	A CRF is a set of printed, optical or electronic documents for each subject on which information to be reported to the sponsor is recorded, as required by the CIP.				

Central independent blinded photographic reviewer (study-specific definition)	Person responsible for MVDSS evaluations; will be dislocated from the investigation sites and will not discuss any findings with the investigators during the investigation
Clinical Investigation	The terms 'clinical trial' or 'clinical study' are synonymous with 'clinical investigation'.
Clinical Investigation Plan (CIP)	Document that states the rationale, objectives, design and pre- specified analysis, methodology, organization, monitoring conduct and record-keeping of the clinical investigation.
	Study-specific addition: For the purpose of this document "protocol" is synonymous with "CIP".
Comparator (device)	Medical device, therapy (e.g., active treatment, normal clinical practice), used in the control group in a clinical investigation.
Coordinating Investigator (CI)	A Coordinating Investigator is appointed by the sponsor to assist in coordinating the work in a multicentre clinical investigation.
Concomitant Treatment (study-specific definition)	All medications taken and non-pharmacological procedures applied by a subject during the course of a clinical study. Further details see "Prior Treatment".
Deviation	Instance(s) of failure to follow, intentionally or unintentionally, the requirements of the CIP.
Device Deficiency	A device deficiency is an inadequacy of a medical device with respect to its identity, quality, durability, reliability, usability, safety or performance.
	Device deficiencies include malfunctions, use errors, and inadequacy in the information supplied by the manufacturer including labelling.
	This definition includes device deficiencies related to the test device or the comparator device.
Effectiveness	Achievement of a clinically significant intended result in a defined portion of the target population when the investigational medical device is used within its intended uses and according to its instructions for use, the investigator's brochure and the CIP, as determined by documented scientific evidence
Ethics Committee (EC)	The Ethics Committee (EC) is an independent body whose responsibility it is to review clinical investigations in order to protect the rights, safety and well-being of human subjects participating in a clinical investigation.
	For the purposes of this document, "ethics committee" is synonymous with "research ethics committee", "independent ethics committee" or "institutional review board". The regulatory requirements pertaining to ethics committees or similar institutions vary by country or region.
Independent	A person not involved in the development of the investigational device or the conduct of a clinical investigation, except for their specifically assigned responsibilities, in order to avoid bias or a conflict of interest.

Investigational Medical Device (IMD)	Medical device being assessed for clinical performance, effectiveness or safety or performance in a clinical investigation. This includes medical devices already on the market that are being evaluated within their intended use in a post-market clinical investigation (interventional or non-interventional).
	Study-specific addition : For the purpose of this document "IMD" is synonymous with "test device".
Investigator	An individual member of the investigation site team designated and supervised by the Principal Investigator at an investigation site to perform clinical-investigation-related procedures or to make important clinical investigation-related and medical treatment decisions. An individual member of the investigation site team can also be called 'sub-investigator' or 'co- investigator'.
Investigator's Brochure (IB)	Compilation of the current clinical and non-clinical information on the investigational medical device(s), relevant to the clinical investigation.
Institutional Review Board (IRB)	See definition for Ethics Committee.
Investigation site	Institution or site where the clinical investigation is carried out. Note: "investigation site" is synonymous with "study site".
Investigator site file (ISF)	Binder(s) maintained at the study site containing all regulatory and study specific documents.
Malfunction	Failure of a medical device to perform in accordance with its intended purpose when used in accordance with the instructions for use, IB or CIP.
Medical History (study- specific definition)	Medical history includes prior and ongoing concomitant diseases and possibly recurring conditions.
	New concomitant diseases, not pre-existing at Screening visit or a worsening in the concomitant diseases will be documented as adverse event (AE).
Point of Enrollment	Time at which, following recruitment but before any clinical investigation-related procedures are undertaken, a subject signs and dates the informed consent form.
Principal Investigator (PI)	The Principal Investigator (PI) is a qualified person responsible for conducting the clinical investigation at an investigation site. If a clinical investigation is conducted by a team of individuals at an investigation site, the PI is responsible for leading the team. Whether this is the responsibility of an individual or an institution can depend on national regulations.

Prior Treatment (study- specific definition)	All medications (prescription and over-the-counter products) taken and non-pharmacological procedures applied prior to Screening Visit that was stopped before the first use of the device (at Baseline) is classified as 'prior treatment'.		
	Treatments used at least once after the first use of a device are classified as 'concomitant treatment'. Note, that a treatment classified as 'concomitant' could already be taken prior to first application of device.		
Randomization	Randomization is a process of assigning subjects to the test device or comparator device using an established recognized statistical method using an element of chance to determine the unforeseeable assignment in order to reduce bias.		
Serious Adverse Device Effect (SADE)	A SADE is an adverse device effect that has resulted in any of the consequences characteristic of a SAE.		
Serious Adverse Event	A SAE is an adverse event that led to any of the following		
	
 
a) death,
 
b) serious deterioration in the health of the subject, users, or other persons as defined by one or more of the following: 
 
a life-threatening illness or injury, or
 
a permanent impairment of a body structure or a body function including chronic diseases, or
 
in-patient or prolonged hospitalization, or
 
medical or surgical intervention to prevent life-threatening illness or injury, or permanent impairment to a body structure or a body structure or a body nuclion,
 
 
 
c) fetal distress, fetal death, a congenital abnormality, or birth defect including physical or mental impairment
 
		
	Planned hospitalization for a pre-existing condition, or a procedure required by the CIP, without serious deterioration in health, is not considered a SAE.		
Serious health threat	Signal from any adverse event or device deficiency that indicates an imminent risk of death or a serious deterioration in the health in subjects, users or other persons, and that requires prompt remedial action for other subjects, users or other persons. This would include events that are of significant and unexpected nature such that they become alarming as a potential serious health hazard or possibility of multiple deaths occurring at short intervals (according to ISO 14155).		
Source Data	Source data are all information in original records, certified copies of original records of clinical findings, observations, or other activities in a clinical investigation, necessary for the reconstruction and evaluation of the clinical investigation. This includes electronic source data initially recorded in an electronic format.		
Source Document	Source documents are printed, optical or electronic document containing source data. Examples include: Hospital records, laboratory notes, device accountability records, photographic negatives, radiographs, records kept at the investigation site, at the laboratories and at the medico-technical departments involved in the clinical investigation.		
---------------------------------------------------------------------	---------------------------------------------------------------------------------------------------------------------------------------------------------------------------------------------------------------------------------------------------------------------------------------------------------------------------------------------------------------------------	--	
Source Records	Collection of source documents containing source data.		
Sponsor	Is an individual, company, institution or organization taking responsibility and liability for the initiation and management of a clinical investigation, and arranging the financial setup.		
Subject	Is an individual who is or becomes a participant in a clinical investigation either as a recipient of the test device or the comparator device.		
Treatment (phase) (study-specific definition)	Baseline treatment: Treatment at Visit 2 is defined as "baseline treatment";		
	Touch-up treatment 1: Optional treatment at Visit 3 is defined as "touch-up treatment 1" (TUP1)		
	Initial treatment (phase): Baseline treatment and touch-up treatment together are defined as "initial treatment"; The study phase between Baseline visit and Visit 9 (SV1) is defined as initial treatment phase.		
	For initial treatment either saypha® VOLUME Lidocaine (test device) or the comparator device and the subject are administered (according to randomization of the subject)		
	Repeat-treatment (phase): Optional treatment (with saypha® VOLUME Lidocaine only) at Visit RT1 is defined as "repeat-treatment". The study phase beginning with repeat-treatment at Visit RT1 and up to Visit RT5 is defined as repeat-treatment phase.		
	Touch-up treatment 2: Optional treatment at Visit RT2 is defined as "touch-up treatment 2" (TUP2)		
	For repeat-treatment only saypha® VOLUME Lidocaine (test device) is administered.		
Treating (unblinded) investigator (study-specific definition)	Responsible for all study related assessments and procedures (except those allocated to the blinded evaluator at the site and the central independent blinded photographic reviewer).		
Trial Master File (TMF)	Binder(s) maintained at the sponsor's (CRO's) office containing all regulatory and study specific documents including the essential documents according to the ISO-GCP Guideline.		
Unanticipated Serious Adverse Device Effect (USADE)	An USADE is a serious adverse device effect which by its nature, incidence, severity (intensity) or outcome has not been identified in the current risk assessment and the current version of the Investigator's brochure (adapted according to ISO 14155)		
	Anticipated serious adverse device effect (ASADE) is an effect which by its nature, incidence, severity or outcome has been identified in the risk assessment.		

For the USA only: Unanticipated Adverse Device Effect (UADE)	The investigational device exemption (IDE) regulations define an unanticipated adverse device effect (UADE) as "any serious adverse effect on health or safety or any life-threatening problem or death caused by, or associated with, a device, if that effect, problem, or death was not previously identified in nature, severity (intensity), or degree of incidence in the investigational plan or application (including a supplementary plan or application), or any other unanticipated serious problem associated with a device that relates to the rights, safety, or welfare of subjects. (according to investigational device exemption (IDE) regulations / 21 CFR 812.3(s))
Use error	A user action or lack of user action while using the medical device that leads a different response than that intended by the manufacturer or expected by the user.
	Use error includes the inability of the user to complete a task. Use errors can result from a mismatch between the characteristics of the user, user interface, task or use environment. Users might be aware or unaware that a use error has occurred. An unexpected physiological response of the subject is not by itself considered a use error: A malfunction of a medical device that causes an unexpected result is not considered a use error.

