#### Emergency unblinding

There will be no special procedure for emergency unblinding because the treating investigator and other study staff will be aware of the treatment allocation. In case, only the blinded evaluator at the site is available in case of an emergency situation, and an unblinding is required, he/she **should** contact the Medical Monitor or the Sponsor first before accessing the subject's medical records for unblinding.

The subjects will know that they have received a hyaluronic acid dermal filler with lidocaine, which is, sufficient level of information needed in case of emergency. However, the subjects will receive a participant card with 24/7 emergency telephone numbers.

Any cases of unblinding will be documented by the site staff.

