# 6.2.4.1 saypha® VOLUME Lidocaine

#### Precautions and Warnings

• According to the IB (section 8.1.5), sensitive skin may be pre-treated using a local anesthetic patch or cream (also see section 6.2.2).

**Note:** Whenever possible (i.e., if the subject agrees) additional topical anesthetic (patch or cream) should be avoided in this investigation to not falsify the pain assessment (see section 6.4.14). In case additional local anesthesia is used, this has to be documented as concomitant treatment in the subject's records and the eCRF.

- The device must not be used if the expiry date has lapsed, or if the integrity of the syringe cannot be verified, of if packaging or contents are damaged (open or shifted tip cap or in an opened or damaged blister, syringe is not stored in its originally sealed blister, needle with a damaged container). In such case follow instructions given in section 14.9.
- The device should only be used with the needles / cannulas and syringe provided by the manufacturer / sponsor's representative (also see section 2.1 and section 6.4.19).
- Do not inject into blood vessels, bones, tendons, ligaments, nerves or muscles. Do not inject the device into naevi. In such cases, subjects should receive prompt medical attention and possibly evaluation by an appropriate health care practitioner specialist should an intravascular injection occur. Also see section 6.2.5 and section 14 for documentation and reporting obligations for AEs. Also see sections 6.3.6, 14.5.4 and 16.1.
- Subjects should be advised not to apply make-up for twelve hours after injection and to avoid prolonged exposure to sunlight and UV; also subjects should not use saunas or Turkish baths for one Week after the injection (also see section 6.3.8).
- Subjects should be advised not to massage the treatment site for a few days following the injection, to avoid the possible risk of product mobility (also see section 6.3.8).
- The device should never be placed in contact with quaternary ammonium compounds (such as benzalkonium chloride solutions) or with medical-surgical instruments that have been in contact with these substances (also see section 4.3).

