## 6.4 Assessments and procedures

Assessments and procedures that will be performed during the investigation are described below. The exact timing of each assessment is indicated in Table 1 to Table 3 and in section 6.5.

It is the treating investigator's obligation to assure documentation of all relevant data in the subject's source record and the eCRF, such as medical history and concomitant diseases, date of enrollment into the clinical investigation, visit dates, results of examinations, application of the device, AEs and device deficiencies.

All subject questionnaires assessing improvement and satisfaction with appearance and outcome (i.e., modified GAIS, FACE-QTM) should preferably be done at the beginning of the respective visit to avoid potential influence of investigator's comments on subject's perception during the visit.

**Important note:** The assessments and procedures described in the following sections must ONLY be conducted by the treating investigator (or trained site staff, if applicable), except for the MVDSS, NLF-SRS and modified GAIS rating, that will be done by the blinded evaluator at the site. The central independent blinded photographic reviewer will conduct MVDSS assessment (see section 6.4.13).

To ensure consistency of effectiveness assessments over the study duration, it is preferred that the same person performs the same assessments on the same subject across all visits.

Treatment-related procedures are described in section 6.2.2, AE and device deficiency collection procedure in section 14.9. All other assessments and procedures are described below.

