#### 6.4.15 Numeric Pain Rating Scale (NPRS) - Pain assessment

After each treatment with the device, the subject will be asked by the treating investigator to quantify the pain associated with the procedure by means of a semi-quantitative 11-point Numeric Pain Rating Scale (NPRS), where "0" corresponds to no pain, and "10" to the worst pain imaginable.[38] Separate pain assessments will be performed for the right and left midface area treated.

Pain intensity will be assessed immediately after injection (approx. +3 min), and at 15 min-intervals (approx.  $\pm 3$  min) after end time of the device administration for 60 min post-treatment by asking the subject one of the following questions, as appropriate:

- "How would you rate the pain you have felt during the treatment, if "0" is no pain at all, and "10" is the worst pain you can imagine?"
- "How would you rate the pain you have felt during recovery from the treatment, if "0" is no pain at all, and "10" is the worst pain you can imagine?"

Subject's response will be recorded on the Pain Assessment Form. If additional local anesthesia is used, this has to be documented on the Pain Assessment Form as well. The subject will be provided with the appropriate questionnaire in local language.

Completed subject's Pain Assessment Form will be considered as source documents and archived in the subject's source record. The results will be transferred into the eCRF.

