#### Secondary effectiveness endpoints

All secondary effectiveness endpoints (see section 5.3.3) will be analyzed in an exploratory manner by means of descriptive statistics.

The descriptive tables will show the statistics described at the top of section 7.3 by time of assessments as well as for the changes from baseline (if applicable).

Concerning the follow-up for initial treatment, the last measurements / assessments before first treatment are defined as baseline. Concerning the time after repeat-treatment, the measurements / assessments at Visit RT1 before first repeat-treatment are defined as baseline.

Assessments on the MVDSS (see section 6.4.13) as well on the modified GAIS (see section 6.4.16) will be presented for each possible category. In addition, shift tables from baseline will be provided for the assessments on the MVDSS.

Concerning nasolabial folds measured by NLF-SRS based on the blinded evaluator's live assessment, shift tables from baseline will be presented for Week 4, 8, 16, 24, 36, and Week 48 after last injection of initial treatment phase.

Volume change measurements will be presented for each of the specified areas of interest (left side, right side, and total) at each time of assessment including change from baseline (see section 6.4.12).

The subject's satisfaction with overall treatment outcome will be evaluated based on the scores for 6 positively worded items that ask the subjects to indicate how they feel about the result of their most recent facial aesthetic procedure (FACE-QTM "Satisfaction with Outcome", see section 6.4.17).

Correspondingly, the subject's satisfaction with overall midface augmentation will be evaluated based on the scores for 5 items concerning the appearance of cheeks (FACE-QTM "Satisfaction with Cheeks", see section 6.4.18).

Concerning each injection, the subject's assessment of pain intensity on the Numeric Pain Rating Scale will be described at each time of assessment (immediately after the injection and after 15-minute intervals up to 60 minutes post-treatment) (see section 6.4.14).

The injection volume applied (right midface, left midface, and total), the duration of each injection as well as the injection technique and details concerning the injection equipment will be summarized for each injection time point and treatment group (see section 6.4.9).

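### The NPRS pain score is asked for in person by the treating investigator, who knows the device; having subjects mark the existing form unaided would remove that influence at little cost

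*Protocol*

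**What the plan says.** Protocol section 6.4.15 states that after each treatment "the subject will be asked by the treating investigator to quantify the pain associated with the procedure". Ratings are taken immediately after injection and every 15 minutes up to 60 minutes, separately for left and right. There are two set questions, one on the treatment and one on recovery, each beginning "How would you rate the pain you have felt". As to the record, "Subject's response will be recorded on the Pain Assessment Form", and the subject is given the questionnaire in the local language.

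The treating investigator is the unblinded role. The glossary describes that person as "Responsible for all study related assessments and procedures (except those allocated to the blinded evaluator at the site" and also excepts the central photographic reviewer's work. Section 6.1.3, under emergency unblinding, confirms that "the treating investigator and other study staff will be aware of the treatment allocation". Section 6.1.4 leaves injection volume, technique and equipment to the same person.

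Pain on the 11-point scale is a secondary effectiveness endpoint of the initial phase (5.3.3.1), and 5.2.2.1 has all initial-phase secondary objectives evaluated against the comparator.

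Other subject ratings are handled differently. Section 6.4 says that the modified GAIS and FACE-Q questionnaires "should preferably be done at the beginning of the respective visit to avoid potential influence of investigator's comments on subject's perception". Injection site reactions, including pain after injection, are entered by the subject in an electronic diary (6.4.19).

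**The concern.** The subject is blinded but gives the score in person to someone who knows which device was used and has just treated them. Tone, emphasis, prompting or a remark between questions can move a self-reported score, and someone who knows the allocation can do this differently for the two devices without intending to. A shift common to both arms cancels in the comparison; a differential one does not. It could create or mask a difference in pain between two fillers that both contain 0.3% lidocaine.

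The protocol recognises this kind of influence for the GAIS and FACE-Q but provides nothing equivalent for the NPRS.

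**Working it through.** The point rests on the text. The protocol states no figure for pain that could be reproduced.

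**Passages side by side**

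| Subject-rated measure | How it is obtained | Protection against investigator influence |
|---|---|---|
| Modified GAIS, FACE-Q | Questionnaire answered by the subject (6.4.16 to 6.4.18) | Preferably at the start of the visit (6.4) |
| Injection site reactions | Electronic diary entered by the subject (6.4.19) | Self-recorded, away from the investigator |
| NPRS pain | Treating investigator asks (6.4.15) | Set questions; subject blinding and non-disclosure (6.1.3) |

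Section 6.4 excepts only the MVDSS, NLF-SRS and modified GAIS ratings from the treating investigator's tasks, plus the central photographic review. Pain stays with that person or, where applicable, trained site staff. Under 6.1.3 the site has two kinds of personnel, the blinded evaluator and unblinded staff, so delegation within this rule does not bring in a person unaware of the device.

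Time points per session: immediately, then 15, 30, 45 and 60 minutes, which makes 5.

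**Scale of a bias that would matter (illustration only)**

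Inputs: 324 and 162 subjects randomised (6.3.1). The standard deviation of the pain score is not in the protocol; 1.5 to 3.0 points is assumed.

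95% half-width for a difference in means = 1.96 × SD × √(1/324 + 1/162), with √(1/324 + 1/162) = 0.0962.

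| Assumed SD | Standard error | Half-width |
|---|---|---|
| 1.5 | 0.144 | 0.28 |
| 2.0 | 0.192 | 0.38 |
| 2.5 | 0.241 | 0.47 |
| 3.0 | 0.289 | 0.57 |

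If the devices truly did not differ, an average between-device elicitation shift of about 0.3 to 0.6 points on the 0 to 10 scale would equal the half-width, which is enough to bring such an interval to the edge of excluding zero. This shows how small a differential shift would need to be. It is not evidence that one of that size occurs.

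**The case against.** Much of the case for leaving the procedure alone is sound. Subjects are blindfolded during treatment, the device must be removed or covered before the mask comes off, and staff may not disclose it (6.1.3). The questions are fixed word for word. The start-of-visit rule for GAIS and FACE-Q is only a preference, and it cannot be carried over to pain, which has to be rated after the injection. Section 6.1.4 treats adverse event collection as the main source on the occurrence of pain, and the diary gives a further pain record that the investigator does not elicit. Pain is analysed descriptively and is not among the main secondary endpoints that 7.3.7 lists for between-group 95% confidence intervals. All of this stands and limits the point. It does not change the fact that a device-aware person asks for the score when the subject could mark it alone.

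Three stronger readings are tempting, and the documents do not support them.

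- A reader might infer that pain is pooled over all injections. Section 7.3.7 says otherwise: "Concerning each injection, the subject's assessment of pain intensity on the Numeric Pain Rating Scale will be described at each time of assessment".
- A reader might infer that topical anaesthetic undermines the comparison, because the protocol says "additional topical anesthetic (patch or cream) should be avoided in this investigation to not falsify the pain assessment". But its use is recorded on the pain form and as concomitant treatment (6.2.2, 6.4.15), and concomitant treatments are tabulated (7.3.6). A split by anaesthetic use is a detail for the SAP. It would also condition on something decided after randomisation at touch-up and possibly related to the device, so it would not repair the comparison.
- A reader might infer that 6.4.15 contradicts itself by having the investigator ask while the subject receives the questionnaire. The two are compatible.

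**Conclusion.** The point holds as a modest weakness of design. Section 6.4.15 has the unblinded treating investigator ask for every NPRS score, and the existing safeguards reduce interviewer influence without removing it. It affects one descriptive secondary endpoint, and only in the initial phase, because the repeat-treatment phase uses the test device alone. The primary endpoint, the blinded evaluator's live MVDSS, is unaffected, and no confirmatory decision depends on pain.

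The size of any bias is unknown. The 0.3 to 0.6 point benchmark rests wholly on assumed standard deviations and the planned group sizes. It would be wrong to conclude that the pain comparison is biased; the documents show only an avoidable route by which it could be. The change is desirable rather than essential.

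**What to change.** Amend section 6.4.15 so that at each time point the subject reads the applicable set question and marks the Pain Assessment Form unaided, for left and right, with the device already removed or covered as 6.1.3 requires. The treating investigator does not ask for, read out or comment on the score, and site staff only hand over and collect the form.

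The cost is a short change to one section. The form and the questions already exist, and no extra staff or visits are needed. The one small drawback is that the first score, due at about 3 minutes, may come slightly later because the blindfold must be off. No change to 7.3.7 is needed on this account.

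If initial-phase treatments are already complete, the amendment cannot alter those scores. The clinical investigation report should then state who elicited them, so that the pain comparison is read accordingly.
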